2.3.3 SECONDARY OUTCOME – RESPONSE TIME

RATIONALE. Participants make a button press on a keyboard to indicate if the probed items are matched or non-matched to the items held in memory. The investigators will calculate the response time for each condition. Theta oscillations are known to be generated in frontal cortex when cued to the contralateral visual field. Alpha oscillations are known to be generated in parietal cortex when cued to the ipsilateral visual field.

ALTERNATIVE HYPOTHESIS. When the frequency of TMS to either frontal or parietal cortex is compatible with the endogenous activity, response time should decrease relative to TMS that is incompatible. Therefore, we will report the TMS compatibility effect as the average of "theta minus alpha TMS to frontal cortex for retro-cue right" and "alpha minus theta TMS to parietal cortex for retro-cue left". We will report the mean and standard deviation of the TMS compatibility effect across participants. This effect will be investigated using repeated-measures two-way ANOVA, and an interaction between TMS site and TMS frequency is hypothesized.

NULL HYPOTHESIS. There is no systematic effect of frequency specific TMS on response time.

3 PARTICIPANT SELECTION AND WITHDRAWAL

A total of 48 participants will complete this study and all data will be collected at UNC-CH. No specific plans have been made to enroll participants from vulnerable populations.

3.1 INCLUSION CRITERIA

In order to be eligible to participate in this study, a participant must meet all of the following criteria:

- Between the ages of 18 and 35
- Right handed
- Able to provide informed consent
- Have normal to corrected vision
- Willing to comply with all study procedures and be available for the duration of the study
- Speak and understand English

3.2 EXCLUSION CRITERIA

A potential participant who meets any of the following criteria will be excluded from participation in the study:

- ADHD (currently under treatment)
- Neurological disorders and conditions, including, but not limited to:
 - History of epilepsy
 - Seizures (except childhood febrile seizures)
 - Dementia
 - History of stroke
 - Parkinson's disease
 - Multiple sclerosis
 - Cerebral aneurysm
 - Brain tumors
- Medical or neurological illness or treatment for a medical disorder that could interfere with study participation (e.g., unstable cardiac disease, HIV/AIDS, malignancy, liver or renal impairment)
- Prior brain surgery
- Any brain devices/implants, including cochlear implants and aneurysm clips
- History of current traumatic brain injury
- (For females) Pregnancy or breast feeding
- Anything that, in the opinion of the investigator, would place the participant at increased risk or preclude the participant's full compliance with or completion of the study

Justifications for any exclusions based on race, gender, or ethnicity: There are no exclusion criteria based on race, gender, or ethnicity. However, non-English speaking individuals are excluded because the ability to accurately and completely communicate study information, answer questions about the study, and obtain consent are necessary.

Justification for excluding women or women who become pregnant: Pregnant participants will be excluded despite the fact that theoretical risk to mother or fetus is exceedingly small, since no safety data for pregnancy is known to exist for TMS studies. Female participants will be asked if there is a possibility that they are pregnant at every stimulation session. If the participant says yes or is unsure, then we will verify pregnancy status via a urine pregnancy test. Only upon a verbal confirmation that pregnancy is not possible or a negative finding will we proceed with the experiment.

3.3 STRATEGIES FOR RECRUITMENT AND RETENTION

CONFIDENTIAL

3.3.1 RECRUITMENT

The target population of this study includes healthy individuals between the ages of 18 to 35 recruited from UNC Chapel Hill and the surrounding area, including approximately 30,000 candidates for participation. Recruitment will occur via two methods: flyers to be distributed at major locations on the campus (libraries, gyms, classroom buildings, etc.) and a mass email to all individuals with a UNC-affiliated email address.

3.3.2 RETENTION

Our retention strategy includes a payment schedule of one time per session per participant. The payment amount increases with each session to encourage study completion. The participant will receive payment at the end of each session. The research staff will also give each participant a reminder call or email for upcoming sessions. Each research staff member will be available for the participants to contact via email or phone.

4 BASIC STUDY DESIGN

This study is a pilot, four-session study with TMS and EEG to understand the neural oscillatory basis of cognitive control. Participants will perform a cognitive control task in which a retro-cue is used to distinguish between relevant and irrelevant lateralized stimuli that need to be accurately recalled for testing in each trial. The rhythmic TMS manipulation targets the previously localized EEG frequencies and previously localized regions of the brain from MEG (Wallis et al., 2015). The frequencies of stimulation will be theta (5 hertz), alpha (10 hertz), and arrhythmic. The regions of stimulation will be anterior-MFG, inferior-IPS. The study consists of an initial screening session, a baseline session, and two counterbalanced stimulation sessions with TMS delivered during task performance. During the initial screening session, participants will learn and perform the cognitive control task at varying levels of difficulty in order to titrate their performance accuracy. During the baseline session, participants will perform the titrated cognitive control task while EEG is recorded. The motor threshold (MT) for each participant will also be calculated either on this day or during the Stimulation 1 session. MT is calculated by placing the TMS coil at a 45-degree angle from the midline along the central sulcus (just above the ears). An electrode is attached to the contralateral first dorsal interosseous muscle. Then the primary motor cortex is stimulated with single pulse TMS until a motor evoked potential (MEP) is generated in the contralateral hand muscle, defined as a near-instantaneous increase in electrical activity above 200 microvolts. Then the intensity of TMS is lowered until an MEP is evoked on five out of ten pulses. Additionally, visible hand twitches may be used as instead of visual twitches to determine MT. The MT allows for TMS to be calibrated to the particular sensitivity level of the individual participant's brain. On the subsequent TMS session we will stimulate at 110% of MT. We ensure that TMS is driving neural activity but that this activity is within the range of endogenous activity and hence is at an appropriately safety level according to guidelines established for TMS (Rossi et al. 2009). On the third and fourth session (Stimulation 1 and Stimulation 2) the anterior-MFG and inferior-IPS is targeted by rhythmic TMS during performance of the cognitive control task. The sequence of TMS targets will be randomized and counterbalanced across participants. However, it is not possible to double-blind the study because the location of the TMS coil needs to be aligned to the targeted brain region with neuro-navigation software (Localite, Sankt Augustin, Germany). In other words, the region targeted by TMS is necessarily visible to the experimenter for accurate targeting. The study will be single blinded as the participant will not know the anatomical differences between the targeted regions and the position on the scalp differs by only a few centimeters between each site. Critically, the manipulation of interest is the frequency of stimulation. On each trial, the frequency will be randomly selected, counter-balanced, and inter-mixed. The effects of rhythmic TMS do not last for more than a few cycles beyond stimulation itself (Thut et al. 2011; Hanslmayr et al. 2014; Albouy et al. 2017). Therefore, the experimental design randomly intermixes the frequency of stimulation within every task block. The critical analysis is the within participant comparison of frequency specific TMS effects for a single site. The sequence order of target sites will have no impact because all analyses will be run as a difference from our active control (arrhythmic TMS) from within the same session. In addition, a brief resting-state EEG recording will be collected at the beginning of the

baseline and stimulation sessions.

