Short Title	PATRC
Protocol Number	18-1789
Phase	Pilot
Methodology	Four-session, crossover design, active sham controlled
Study Duration	This study is expected to last eighteen months.
Study Center(s)	This is a four-session and single-site study performed at The University of North Carolina at Chapel Hill.
Objectives (Purpose)	The purpose of this pilot study is to modulate oscillatory activity in the prefrontal cortex using rhythmic transcranial magnetic stimulation during performance of a cognitive control task.
Number of Participants	100 (until 48 are completed)
Diagnosis and Main Inclusion Criteria	Eligible participants will be healthy adults between the ages of 18-35 with no history of mental or psychiatric disorder.
Description of Intervention (Procedures/methods)	The participants will perform a cognitive control task. During the task, rhythmic trains of transcranial magnetic stimulation will be delivered. Electroencephalography will be collected throughout every session.
Related IRB Applications	17-0149

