4.1 TREATMENT ASSIGNMENT PROCEDURES

The three frequencies of interest (theta, alpha, and arrhythmic) are randomly intermixed within every task block. The randomization is uniquely generated for each participant and session. The order of regions targeted (a-MFG and i-IPS) will be randomized and counterbalanced across participants. The primary analysis of the experiment is to analyze the frequency specific effect of rhythmic TMS versus arrhythmic TMS within the same session. Therefore, the experiment is designed such that sequence order is irrelevant as every analysis is performed as a within session difference. Using neuro-navigation software, precludes a double-blinding as the experimenter must be aware of the targeted region. The participant will not be keen to the anatomical differences between these regions that are separated by only a few centimeters.

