11.1 STATISTICAL ANALYSIS STRATEGIES

To control for non-specific effects of rhythmic TMS, we will use an active control: arrhythmic TMS (randomized inter-pulse-interval) that is matched to the target stimulation in number of pulses and temporal duration. All analyses will be run on the difference from condition-matched arrhythmic TMS. The key analysis is a two-way repeated-measures ANOVA with factors TMS frequency (theta vs alpha) and location (inferior-IPS vs anterior-MFG). Post-hoc t-tests will be run on a significant main effect of TMS frequency, TMS site, or interaction. We will use Tukey's adjusted significance for post-hoc testing to correct for multiple comparisons.

Primary outcome: working memory capacity. Two-way repeated-measures ANOVA run on the difference from arrhythmic TMS with factors (TMS site and TMS frequency). The direction of the retro-cue is held consistent for each site: for TMS to frontal cortex (anterior-MFG) the retro-cue to the right is used, and for TMS to parietal cortex (inferior-IPS) the retro-cue to the left is used. We hypothesize that theta frequency rhythmic TMS will improve behavioral performance when applied to anterior-MFG; i.e. a main effect of TMS frequency and/or an interaction between TMS frequency and cue. We hypothesize that alpha frequency rhythmic TMS will improve behavioral performance for retro-cue trials when applied to inferior-IPS; i.e. an interaction between TMS frequency and cue.

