11.2 SAMPLE SIZE DETERMINATION

Based on a previous study with the current behavioral paradigm and similar TMS manipulation, the effect size of the interaction between TMS site and TMS frequency on WM capacity was 0.532 and used 21 participants. A power analysis of this effect suggests that to reach 95% statistical power we would need to recruit 48 participants. Therefore, we will run our final analysis on 48 participants. Previous studies using a similar methodology of concurrent rhythmic TMS and EEG to look for changes in oscillatory power of the frequency of rhythmic TMS have used 10 participants for alpha frequency TMS (Thut et al., 2011) and 17 participants for theta rhythmic TMS (Albouy et al. 2017). Here, we propose to collect 48 participants. Therefore, our statistical power exceeds that of previous studies published in high-impact journals using a nearly identical methodology. Furthermore, we utilize a repeated-measures inter-mixed design in order to maximize our ability to control for confounding variables and increase statistical power. Based on a previous study by Thut et al., 2011 that found an increase in alpha oscillatory power from alpha rhythmic TMS relative to arrhythmic TMS with an effect size of 0.83 and 10 participants, we would need 21 participants to reach 95% statistical power for this comparison. Based on a previous study by Albouy et al., 2017 that found an increase in theta oscillatory power from theta rhythmic TMS relative to arrhythmic TMS with an effect size of 0.56 and 17 participants, we would need 44 participants to reach 95% statistical power for this comparison. Therefore, we estimate that based on these previously reported effect sizes for the impact of rhythmic TMS on behavior and oscillatory power measured by EEG in similar studies and our proposed sample size of 48 participants, we conclude that the proposed study has sufficient statistical power to answer the posed hypotheses.

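### Site order is declared irrelevant, but the key site-by-frequency test compares two sessions: leaving order out can cost power, and can bias the interaction if order is unbalanced among completers

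*Combined protocol and SAP*

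**What the plan says.** Section 4 (Basic study design) places the two targets, anterior MFG and inferior IPS, in separate stimulation sessions, with their sequence randomised and counterbalanced over participants. It then says "The sequence order of target sites will have no impact because all analyses will be run as a difference from our active control". Section 4.1 repeats the point: "the experiment is designed such that sequence order is irrelevant as every analysis is performed as a within session difference".

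Section 11.1 says "The key analysis is a two-way repeated-measures ANOVA with factors TMS frequency (theta vs alpha) and location (inferior-IPS vs anterior-MFG"). For working memory capacity it specifies "Two-way repeated-measures ANOVA run on the difference from arrhythmic TMS with factors (TMS site and TMS frequency"). No session, order or sequence term appears anywhere in section 11. Sections 2.3.1 to 2.3.3 each hypothesise the site-by-frequency interaction. Section 11.2 sizes the trial on it: "the effect size of the interaction between TMS site and TMS frequency on WM capacity was 0.532 and used 21 participants", and "A power analysis of this effect suggests that to reach 95% statistical power we would need to recruit 48 participants".

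The Study Summary gives the number of participants as "100 (until 48 are completed"). No block size is stated for the order randomisation, and no rule keeps the two orders equal among those who complete.

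**The concern.** The reason given for ignoring order is that every analysis is a difference taken inside one session. For the key test this is not so. Each participant has one site in Stimulation 1 and the other in Stimulation 2, so the interaction is a theta-minus-alpha difference from one session minus the same difference from the other. Anything that changes the frequency effect between the two sessions, such as habituation to the trains or a change of task strategy, enters the contrast with opposite signs in the two order groups.

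Two things are at stake. Left unmodelled, such a change inflates the error variance. If the two orders are also unequal in number among the 48 analysed, it shifts the estimate. Both can be avoided using groups the trial already randomises.

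**Working it through.** **Inputs.** From section 11.2: effect size 0.532, 95% power, N = 48. Alpha and sidedness are not stated; two-sided 0.05 is assumed. Two stimulation sessions are taken from sections 4 and 5.2 and Appendix A. Section 6.2 implies three sessions with rhythmic trains, which must be reconciled. The session shift p is not in the documents, so a range is shown.

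**Step 1: the plan's own figure.** The interaction in a 2×2 repeated-measures ANOVA is a one-sample t-test on each participant's contrast

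D = (theta − alpha) at MFG − (theta − alpha) at IPS.

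Reading 0.532 as mean/SD of D, the noncentrality is 0.532 × √48 = 3.686 on 47 df, and power is 0.9505. The smallest N reaching 95% is 48, so the stated figure reproduces. (A one-sided test would need 40.) The compatibility effect in section 2.3.1 is D/2, so it is the same test.

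**Step 2: what the arrhythmic subtraction does.** Let A be the arrhythmic value in a site's session. Then (theta − A) − (alpha − A) = theta − alpha. A drops out at each site, so D is the same with or without the subtraction. A session effect common to all frequencies cancels anyway; a session-by-frequency effect does not.

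**Step 3: model.** Let p be the change in theta − alpha from Stimulation 1 to Stimulation 2, in SDs of D within an order group. Then

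D = δ + s·p + e, with s = +1 (parietal first) or −1 (frontal first) and SD(e) = 1.

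With n1 and n2 completers per order and w = (n1 − n2)/48, the mean of D has expectation δ + p·w and standard error 1/√48. Without an order term, the residual sum of squares is noncentral chi-square on 47 df with noncentrality 48p²(1 − w²). Because the group sizes are fixed, p does not add noise to the mean; it only inflates the estimated SD. Rejection rates follow by integrating over that distribution, and simulation of the same model agrees within 0.2 percentage points.

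**Step 4: no order term, 24/24 (w = 0, bias 0).**

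| p | Power | Type I error |
|---|---|---|
| 0 | 95.0% | 5.0% |
| 0.1 | 94.9% | 4.9% |
| 0.25 | 94.4% | 4.3% |
| 0.5 | 92.0% | 2.9% |
| 1.0 | 79.1% | 0.6% |

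**Step 5: no order term, unequal completers.** Bias = p(n1 − n2)/48.

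| Split | p | Bias (SD) | Share of 0.532 | Type I error |
|---|---|---|---|---|
| 28/20 | 0.25 | 0.25 × 8/48 = 0.042 | 8% | 5.2% |
| 28/20 | 0.5 | 0.5 × 8/48 = 0.083 | 16% | 5.6% |
| 32/16 | 0.25 | 0.25 × 16/48 = 0.083 | 16% | 7.9% |
| 32/16 | 0.5 | 0.5 × 16/48 = 0.167 | 31% | about 15% |

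**Step 6: with the order term.** The estimate is the unweighted mean of the two order-group means of D. Its standard error is ½√(1/n1 + 1/n2), on 46 df. Bias is zero and type I error 5.0% whatever p is. Power is:

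- 24/24: SE 0.1443, noncentrality 3.686, power 95.0% (0.9503 against 0.9505 on 47 df)
- 28/20: SE 0.1464, noncentrality 3.634, power 94.5%
- 32/16: SE 0.1531, noncentrality 3.475, power 92.5%

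**Step 7: if 0.532 already contains the order variance.** If the earlier study also left order out, with equal orders, the within-order effect is 0.532√(1 + p²): 0.548 at p = 0.25 and 0.595 at p = 0.5. Planned power is then not reduced. Adding the term would raise it to 96.1% or 98.1%.

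**The case against.** The harm is conditional. It needs the frequency effect itself to change between sessions, and the documents neither report nor quantify such a change. Frequencies are intermixed within every block, so general practice, fatigue or habituation falls on theta and alpha alike and cancels. Participants have also met the task in two earlier sessions. At p = 0.1 the power loss is about 0.1 point. Bias needs a second condition, imbalance among completers, whereas the plan says order is counterbalanced; the 28/20 and 32/16 splits are illustrations. Section 4 also calls the single-site comparison the critical analysis, and section 4.1 calls rhythmic against arrhythmic within a session the primary one. For those contrasts the differencing does remove additive session effects.

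All of this stands as a limit on size. It does not rescue the stated reason. Interaction is the hypothesis in section 2.3, the key analysis in section 11.1 and the basis of the sample size, and within-session differencing does not protect it. The remark in section 4 that stimulation effects last only a few cycles concerns carry-over, not change between sessions.

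A reader might infer that the interaction is biased, or that the trial is underpowered. The documents support neither. With 24/24 completers the unadjusted test is unbiased and conservative, and the Study Summary shows only that balance among completers is not guaranteed, not that it will fail.

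**Conclusion.** The point holds in conditional form. The statements in sections 4 and 4.1 do not apply to the test the trial is powered for. Leaving order out can cost power: under 1 point for a shift up to 0.25 SD, about 3 points at 0.5 SD and about 16 points at 1.0 SD, when completers are 24/24. It can bias the interaction only if a shift exists and order is also unbalanced. Type I error then stays near nominal at 28/20 but reaches about 15% at 32/16 with p = 0.5.

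These sizes rest on an assumed p, two-sided 0.05, two stimulation sessions, and 0.532 being the effect relative to the within-order SD. The case for change rests less on the likely loss, which may be small or nil, than on the fact that the protection costs almost nothing and is best fixed before the data are seen.

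**What to change.** - In section 11.1, add site order (frontal first or parietal first) as a between-participant factor in each ANOVA, crossed with site and frequency. Test the site-by-frequency interaction averaged with equal weight over the two orders. Cost: SAP wording and one degree of freedom (power 0.9505 to 0.9503 at 24/24), with no extra participants.
- State that a participant enrolled to replace a non-completer takes that person's site order, so the 48 completers stay close to 24/24.
- In sections 4 and 4.1, limit the statements on order to additive session effects in single-site, within-session contrasts.
- Reconcile which analysis is primary: sections 4 and 4.1 on one side, sections 2.3, 11.1 and 11.2 on the other. Reconcile also the number of rhythmic-stimulation sessions in section 6.2 with sections 4 and 5.2, since the order factor depends on it.
- Do not present the order term as a remedy for unequal carry-over between the two sequences. It does not remove that; the plan's argument there remains the short duration of the stimulation effect.

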4.1 TREATMENT ASSIGNMENT PROCEDURES

The three frequencies of interest (theta, alpha, and arrhythmic) are randomly intermixed within every task block. The randomization is uniquely generated for each participant and session. The order of regions targeted (a-MFG and i-IPS) will be randomized and counterbalanced across participants. The primary analysis of the experiment is to analyze the frequency specific effect of rhythmic TMS versus arrhythmic TMS within the same session. Therefore, the experiment is designed such that sequence order is irrelevant as every analysis is performed as a within session difference. Using neuro-navigation software, precludes a double-blinding as the experimenter must be aware of the targeted region. The participant will not be keen to the anatomical differences between these regions that are separated by only a few centimeters.

